## 1.0 Objectives / Specific Aims

A primary cause of relapse to cocaine use is the high motivation to seek drug produced by cocaine-associated cues. Cue-induced craving is associated with cue-induced elevated corticostriatal activity. Preclinical models demonstrate that decreasing activity in the medial prefrontal cortex (mPFC) and ventral striatum (i.e. nucleus accumbens core), henceforth the “corticostriatal circuit,” can block cue-induced cocaine seeking. As an extension of these preclinical data, the scientific premise of Project 4 is that targeted inhibition of the corticostriatal circuit will dampen cue-induced cocaine craving in individuals with cocaine use disorder.

The overarching goal of this project is to evaluate the efficacy of continuous theta burst stimulation (cTBS) as a tool to restore corticostriatal circuitry function and dampen cocaine cue reactivity among treatment-engaged individuals. cTBS is a non-invasive brain stimulation tool that induces long-term depression (LTD) of neural excitability in the area stimulated and in monosynaptic targets. Recent data from our group demonstrates that a single dose of cTBS to the mPFC selectively decreases activity in the ventral striatum and craving. The efficacy of cTBS as a tool to modulate the striatum depends upon connectivity between the frontal cortex and the striatum. Specifically, the experiments described in this proposal will determine if LTD-like cTBS delivered over mPFC decreases cocaine cue reactivity in individuals with cocaine use disorder. We will evaluate our novel intervention through a double blinded (ACTIVE cTBS vs. SHAM;) study in 160 cocaine dependent individuals. The chance of being randomly assigned to any given group within one of the two treatment arms is 1:1. All individuals will undergo a screening visit (Visit 1; V1), and a baseline fMRI visit (Visit 2; V2) that will assess rsFC and drug cue-reactivity. Following Visit 2, individuals will be randomly assigned to one of 2 to receive either: 1) Active cTBS alone, or 2) Sham cTBS alone. Both groups of participants will undergo a second fMRI visit (Visit 3; V3) that will assess resting-state and drug cue-reactivity: once at the beginning of the session and again immediately following Active cTBS or Sham cTBS. Research staff will follow-up with participants via phone to assess current drug use and craving at 1-day, 1-week, 2-week and 3-weeks post-V3.

**Aim – To evaluate mPFC cTBS as a tool to modulate corticostriatal rsFC and drug cue reactivity in treatment-seeking cocaine users.** *Rationale:* Drug cues reliably activate the mPFC & striatum in multiple classes of substance users, including cocaine users. This contributes to craving and subsequent relapse. Through an LTD-like form of cTBS it is possible to decrease activity in the mPFC and the striatum and dampen self-reported craving in chronic cocaine users. *Hypothesis:* LTD-like cTBS to the mPFC of individuals with cocaine use disorder will decrease cocaine cue-reactivity BOLD response in corticostriatal nodes (i.e. mPFC, ventral striatum) and enhance corticostriatal rsFC.

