## 3.0 Intervention to be studied

Transcranial magnetic stimulation (TMS) is an FDA-approved, non-pharmacological intervention for Depression, OCD, and Smoking Cessation. It is a non-invasive form of brain stimulation that delivers magnetic pulses to the human brain to change brain excitability, and ultimately change behavior. TMS is not FDA-approved for cocaine use disorder, however PI [name] is a leading expert in brain stimulation and the MUSC IRB, as well as the FDA, have determined repetitive TMS to be a non-significant risk intervention. A specific form (parameter) of TMS known as continuous theta burst stimulation (cTBS) will be utilized as the intervention in this study.

Potential Risks of TMS are minor, however include:

- 1). Potential risk of a seizure: The major risk using repetitive TMS subjects is the possibility of inducing a seizure. We have now studied and given rTMS to more than several hundred subjects over past 15 years. None of these patients has developed a seizure. We will exclude patients with a prior history of seizures.
- 2). Potential for scalp discomfort and headaches: Some people report mild discomfort when the magnetic pulses are applied over the scalp. A small number of people (~5%) report headache following TMS. However, the headaches are temporary and manageable with common over-the-counter pain remedies.
- 3). Potential hearing loss: The discharge of the rTMS coil generates a high-energy click that may cause cochlear damage. Foam earplugs can protect against these changes and will be worn by the subjects and the researchers present during TMS sessions.

The research team is highly experienced in administering TMS and [name] has been administering TMS for over 10 years in thousands of sessions. Furthermore, the team will properly pre-screen participants to ensure safety and minimize risk.

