### Exclusion Criteria

1. Past head injury or primary neurological disorder associated with MRI abnormalities, including dementia, MCI, brain tumors, epilepsy, Parkinson's disease, or demyelinating diseases
2. Any physical or intellectual disability affecting completion of assessments
3. Any contraindication to MRI
4. Current or past psychosis
5. ECT in last 6 months
6. Among females, pregnancy at screening will be exclusionary. Females of child bearing potential must agree to undergo a pregnancy test 72 hours prior to the fMRI scanning session and regularly before and during the medication trial. They must further agree to notify the study physician or PA if they become pregnant during the study.
7. Clinical Institute Withdrawal Assessment (CIWA-Ar) scale will be used to assess alcohol withdrawal. Individuals with CIWA > 8 will be excluded.

8. Individuals with unstable medical illness (e.g., hypertension, diabetes, myocardial infarction)
9. Has current suicidal ideation or homicidal ideation.
10. Has the need for maintenance or acute treatment with any psychoactive medication including anti-seizure medications and medications for ADHD
11. Suffers from chronic migraines
12. Any physical or intellectual disability affecting completion of assessments

We will not be enrolling vulnerable populations, specifically pregnant women, children, prisoners, or institutionalized individuals. We also will not enroll subjects incapable of providing their own consent. Should a potential subject present where there is a concern about their ability to understand study procedures and provide meaningful consent, their cognitive status and understanding of the study will be evaluated by [name] (Co-I). If there is any concern that the individual may be impaired, they will not be eligible for participation and not enrolled in the study. The rationale will be provided to the individual as well as his or her family members. Referrals for further evaluation, including urgent or emergent evaluation, will be made as needed and clinically warranted.

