
will have an MRI before and after cTBS. Individuals will be followed up with by telephone 1 day, 1 week, 2 weeks and 3 weeks after their final visit (V3). An informed consent form which details the study requirements, risks, and benefits will be given to the potential research subject to read and sign.

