
Briefly, two trains of either real or sham LTD-like cTBS will be applied over the left frontal pole (EEG 10-20 system: FP1) (1 train: 120 sec, 3 pulse bursts presented at 5Hz, 15 pulses/sec, 1800 pulses/train, 60 sec intertrain interval; 110% RMT, MagPro) using a figure-of- 8 coil (Coil Cool-B65 A/P). During the real and sham cTBS treatment sessions the amplifier output will be escalated (over 30 seconds) from 80% to 110% RMT to enhance tolerability. The MagVenture MagPro system has an integrated, active sham that

passes current through two surface electrodes placed on the scalp. The electrodes will be placed on the left frontalis muscle for all sessions. A patient ID card will randomize participants to receive either real or sham stimulation. This system maintains blinding by a gyroscope in the coil which indicates to the clinical staff whether the coil should be rotated up or down for this participant once the card is entered into the machine. One side of the coil is active, the other is sham. The integrity of the double-blind procedure will be assessed by asking the patients and study personnel rate their confidence regarding their assignment to real or sham TMS (scale 1-10). Immediately after the cTBS session:

- *Confidence in Active or Sham cTBS Assignment (1min)*. Participants will complete a form indicating their confidence (scale 1-10) in whether they are receiving active or sham treatment, and will be prompted to audio record a reason (audio recordings are then transcribed to text, in order to avoid handwriting recognition challenges). Pooled accuracy from prior work in our collaborator's laboratory was 47.6% suggesting that individuals were not aware of the stimulation being received.
- *T1 MPRAGE, Field Map, Resting-State Functional Connectivity, Functional MRI Cocaine Cue Reactivity Task (MRI 3)*: These scans will be repeated exactly as mentioned above for V2 (MRI 1).

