- *Behavioral Assessments*. In order to produce a clinically meaningful effect of TBS on behavioral measures such as drug craving, mood, or usage multiple days (and likely multiple weeks of TBS treatment are required). Therefore, brain based dependent measures are the primary outcomes of the study (as they are sensitive to a single day of real versus sham TBS [39]. For the purpose of being thorough however, we will acquire measurements of cocaine craving (Numerical rating scale 1-10) before, 10, 20, 30 minutes after TBS, as well the demand and value of cocaine as a reinforcer using a delayed discounting task and hypothetical purchasing task (before TBS as well as at the conclusion of the TBS visit).
- *Participant compensation*. Participants will be compensated up to \$250 for completion of all study procedures. Participants will receive \$25 at the screening visit, \$80 for the baseline experimental visit and \$80 for the second fMRI scanning session. Participants will receive \$10 for each follow up phone call, up to \$40 for 1 day, 1 week, 2 weeks and 3 weeks after their last visit. Participants will also receive a \$25 bonus for completion of all study visits, follow ups. Compensation will be made for each session completed and will not be contingent upon completion of the entire study. During the informed consent procedure, participants will be notified that they can withdraw from the study at any time under no penalty. Payment will be made for each session completed and will not be contingent upon completion of the entire study. During the informed consent procedure, participants will be notified that they can withdraw from the study at any time under no penalty.
- *DSM Board Plan*: The PIs and Co-I ([name].) will have overall responsibility for safety and data monitoring on a day-to-day basis. The DSMB, as noted below, will provide guidance and input on a scheduled and as-needed basis. As previously mentioned, the DSM Board will meet every 5-7 months with the PI to discuss the information listed in "Content of ME/DSM report". This content of this meeting will be formalized in a report which will be circulated by email and digitally approved by the PI and ME/DSMB. The approved report will be sent to the MUSC IRB, and to the NIH.

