#### **2. Transcranial Magnetic Stimulation:**

- a. **Investigational Device Exemption:** Transcranial Magnetic Stimulation is an investigational device. The IRB at MUSC (in cooperation with the FDA) have determined repetitive TMS to be a non-significant risk intervention.
- b. **Potential Risks of TMS**
  - 1). **Potential risk of a seizure:** The major risk using repetitive TMS subjects is the possibility of inducing a seizure. We have now studied and given rTMS to more than several hundred subjects over past 15 years. None of these patients has developed a seizure. We will exclude patients with a prior history of seizures.
  - 2). **Potential for scalp discomfort and headaches:** Some people report mild discomfort when the magnetic pulses are applied over the scalp. A small number of people (~5%) report headache following TMS. However, the headaches are temporary and manageable with common over-the-counter pain remedies.
  - 3). **Potential hearing loss:** The discharge of the rTMS coil generates a high-energy click that may cause cochlear damage. Foam earplugs can protect against these changes and will be worn by the subjects and the researchers present during TMS sessions.

**3. Incidental Findings: Magnetic Resonance Imaging:** Some MRI scans can detect medical conditions, such as cancer, brain injury, and abnormal blood vessels; however, this functional MRI is carried out

purely for experimental purposes and we are not looking for brain disorders. Furthermore, the study researchers are not trained in diagnosing brain disorders; therefore, the researchers are not qualified to offer any medical opinions concerning the scan (good or bad). It is possible that the study researchers will notice something in a participant's scan that appears unusual and/or abnormal, if this occurs, the researchers will inform the participant of the finding and provide them with a copy of their scan, which they may take to a medical expert for further review and diagnosis. Being told about such a finding may cause anxiety as well as suggest the need for additional tests and financial costs. Any costs associated with clinical follow-up(s) are the participant's and/or the participant's insurance carrier's responsibility. Participants who do not wish to be informed of such findings will be advised to not participate in this study.

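### No structured harms question is written into the itemised steps after cTBS at Visit 3 or into the four follow-up calls, so headache and hearing effects may be under-recorded in both arms

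*Combined protocol and SAP*

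**What the plan says.** **Named risks.** Sections 3.0 and 15.0 list seizure, scalp discomfort and headache, and hearing loss. Headache has a rate: "A small number of people (~5%) report headache following TMS". Hearing has a mechanism but no rate: "The discharge of the rTMS coil generates a high-energy click that may cause cochlear damage".

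**Follow-up calls.** Section 1.0 gives their purpose: "Research staff will follow-up with participants via phone to assess current drug use and craving". It times them at 1 day and at 1, 2 and 3 weeks after Visit 3. Section 8.0 repeats the four time points and adds nothing about content.

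**Visit 3 after cTBS.** Section 10.0 itemises a blinding check ("Participants will complete a form indicating their confidence (scale 1-10) in whether they are receiving active or sham treatment"), a repeat of the MRI sequences, craving ratings at 10, 20 and 30 minutes, and discounting and purchasing tasks. The overview paragraph of Section 10.0 also promises clinical assessments immediately after cTBS and points to a later list. The Visit 3 text contains no clinical or safety measure of that kind.

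**Other safety text.** The health and physical examination is listed at Visit 1 only. Section 8.0 allows unscheduled evaluations when clinically indicated. Section 15.0, item 5, describes contacting a clinician when a participant expresses worrying symptoms. The DSM Board paragraph in Section 10.0 has the investigators monitor safety day to day. The board meets every 5 to 7 months and "will provide guidance and input on a scheduled and as-needed basis", working from a report content list that is not in the available text.

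**The concern.** The plan names the harms and has contacts at the right times, but gives those contacts another stated purpose. The call one day after stimulation is the natural place to ask about headache or a change in hearing, and its stated content is drug use and craving. A harm that nobody asked about cannot be recovered at analysis.

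Two things are at stake. A participant with a mild but relevant complaint may not be referred to the study physician. And a low count could reflect either good tolerability or not having asked, with nothing in the data to tell the two apart. The board and any later report would face the same ambiguity.

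This is more than brevity. Section 10.0 gives the craving ratings to the minute. Section 13.0, headed as provisions for monitoring data for subject safety, covers sources of material and confidentiality. Section 12.0 plans no tabulation of harms by arm.

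**Working it through.** The documents give no figure for harm ascertainment, so there is none to reproduce. The check has two parts.

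**1. Contacts set against named harms**

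| Contact | Stated content | Harms item written? |
|---|---|---|
| Visit 1 (Section 10.0) | Physical examination, interviews, questionnaires | Clinical assessment, but before stimulation |
| Visit 2 (Section 10.0) | Baseline MRI; clinical assessments promised in overview | Before stimulation |
| Visit 3 after cTBS, itemised steps (Section 10.0) | Blinding form, MRI, craving, two tasks | No |
| Visit 3 clinical assessments (Section 10.0 overview) | Promised, not listed | Unknown |
| Four calls (Sections 1.0 and 8.0) | Drug use and craving | No |
| Unscheduled evaluation (Section 8.0) | When clinically indicated | Needs a prior indication |
| Clinician contact (Section 15.0, item 5) | When symptoms are expressed | Needs a prior complaint or observation |

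No adverse-event definition, grading or collection window appears either. At 144 participants, the calls number 144 × 4 = 576.

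**2. Scale, using headache**

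Inputs:
- Rate of 5% (Sections 3.0 and 15.0), assumed to apply per active participant.
- Arm size n: 160 enrolled or 144 full data sets (Section 6.0), split 1:1 (Section 1.0), so 160/2 = 80 or 144/2 = 72. The two totals agree: 160 × 0.90 = 144.
- Capture share c, the fraction of headaches that reach the record. The documents give none, so c is an assumption shown over a range.

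Formulas: expected recorded = n × 0.05 × c. P(at least one recorded) = 1 − (1 − 0.05c)^n.

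| c (assumed) | n = 72: expected | P(≥1) | n = 80: expected | P(≥1) |
|---|---|---|---|---|
| 1.00 | 3.6 | 97.5% | 4.0 | 98.3% |
| 0.75 | 2.7 | 93.6% | 3.0 | 95.3% |
| 0.50 | 1.8 | 83.8% | 2.0 | 86.8% |
| 0.25 | 0.9 | 59.6% | 1.0 | 63.4% |

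If the 66% eligibility and 90% retention in Section 10.0 apply to the 160, then 160 × 0.66 × 0.90 = 95.04, or about 48 per arm. Full capture then gives 48 × 0.05 = 2.4 expected headaches, and the count is more fragile still.

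Exact (Clopper-Pearson) 95% limits show how the reading of the result depends on a few events: 4/72 gives 1.5% to 13.6%; 1/72 has an upper limit of 7.5%; 0/72 has an upper limit of 5.0%. The counts of 1 and 0 are illustrations of incomplete capture, not predictions.

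**The case against.** The strongest case on the other side is that silence is not a decision. Section 1.0 is an overview sentence and does not say the calls are limited to drug use and craving. The overview in Section 10.0 promises clinical assessments after cTBS, the board's report content is not in the available text, and Section 10.0 refers its safety procedures to earlier publications. Any of these might contain a harms question. Participants also remain with staff after stimulation through about 5 + 1 + 24 + 24 = 54 minutes of MRI sequences, and Section 15.0 says that staff supervise participants closely. The sole endpoint in Section 4.0 is an fMRI change after one session of an intervention classed as non-significant risk, with headaches described as temporary.

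Much of this stands, and it rules out some stronger readings.

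- **That the board would review an undercount.** A reader might infer this, but neither the report content nor the Visit 3 assessments can be seen. The text supports only that counts may be incomplete.
- **That psychiatric harms are counted only if volunteered.** Section 15.0, item 5, describes staff screening, and independent clinician assessment at the examination and at any later clinical interview. Section 8.0 allows unscheduled evaluations. No such interview is scheduled after cTBS, but the stronger claim does not follow. Psychiatric harm is also not among the named stimulation risks; the line "Has current suicidal ideation or homicidal ideation" is an exclusion at entry.
- **That the real-versus-sham comparison of harms would be biased.** Both arms have the same contacts under a double blind with an active sham. If blinding holds, volunteered reporting is less sensitive in both arms, but a difference between arms is not shown.

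What the objection does not remove is that no itemised step after stimulation, and no call, is written to ask. A reference to other publications does not show that these calls ask. Staff presence for about an hour does not cover what a participant notices later.

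**Conclusion.** The point holds as a gap in planned harm ascertainment that should be closed. No structured harms question is written into the itemised post-cTBS steps at Visit 3 or the four calls. Run as written, headache and hearing effects would be recorded mainly if volunteered or noticed, so harms may be under-recorded in both arms and the board may see incomplete counts.

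The size of any shortfall cannot be computed, because the documents give no capture rate. What can be said is that few events are expected: 3.6 to 4.0 headaches among 72 to 80 active participants, if the 5% rate applies to this session. Capture of one half or one quarter, both assumed, would leave about 2 or 1. Full ascertainment would still give a wide interval (1.5% to 13.6% at 4/72), so the gain is a count that can be trusted and prompt referral, not a precise rate.

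The conclusion rests on the unlisted Visit 3 clinical assessments not already containing such a question. If they do, the gap narrows to the calls and to writing the content down.

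**What to change.** Add one short fixed harms questionnaire covering scalp pain, headache, hearing change or tinnitus, seizure-like event, any other new symptom, and any care sought. Give it before cTBS as a baseline, at the end of Visit 3, and at each of the four calls already scheduled. Use the same wording in both arms, asked by staff blinded to assignment. Send positive answers through the clinician-contact pathway already in Section 15.0, item 5.

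In the text, list the Visit 3 clinical assessments that Section 10.0 promises, state how events are defined and graded and over what window they are collected, and say that counts by arm go into the safety board's report.

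The cost is a few minutes per existing contact, one REDCap form and one table, with no new visits. The downside is that more minor events will be recorded in both arms; the baseline administration helps to separate these from complaints that were present before stimulation.

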## 2.0 Background

This project utilizes a multi-disciplinary approach with complementary design features to allow for the bidirectional translation of findings of treatment effects on neurobiology (animal) and neurocognition (human) on corticostriatal circuits. Findings will provide the foundation for identifying individual and combined neural mechanisms of action of cTBS and will inform the optimization of novel individually-guided cTBS for treating cocaine use disorder.

## 3.0 Intervention to be studied

Transcranial magnetic stimulation (TMS) is an FDA-approved, non-pharmacological intervention for Depression, OCD, and Smoking Cessation. It is a non-invasive form of brain stimulation that delivers magnetic pulses to the human brain to change brain excitability, and ultimately change behavior. TMS is not FDA-approved for cocaine use disorder, however PI [name] is a leading expert in brain stimulation and the MUSC IRB, as well as the FDA, have determined repetitive TMS to be a non-significant risk intervention. A specific form (parameter) of TMS known as continuous theta burst stimulation (cTBS) will be utilized as the intervention in this study.

Potential Risks of TMS are minor, however include:

- 1). Potential risk of a seizure: The major risk using repetitive TMS subjects is the possibility of inducing a seizure. We have now studied and given rTMS to more than several hundred subjects over past 15 years. None of these patients has developed a seizure. We will exclude patients with a prior history of seizures.
- 2). Potential for scalp discomfort and headaches: Some people report mild discomfort when the magnetic pulses are applied over the scalp. A small number of people (~5%) report headache following TMS. However, the headaches are temporary and manageable with common over-the-counter pain remedies.
- 3). Potential hearing loss: The discharge of the rTMS coil generates a high-energy click that may cause cochlear damage. Foam earplugs can protect against these changes and will be worn by the subjects and the researchers present during TMS sessions.

The research team is highly experienced in administering TMS and [name] has been administering TMS for over 10 years in thousands of sessions. Furthermore, the team will properly pre-screen participants to ensure safety and minimize risk.

